This is a retrospective controlled survey-study to assess the safety of treating migraine with Nerivio during pregnancy and 3 months postpartum. We will compare migraine and pregnancy related health and baby health between women with migraine who treated migraine attacks during pregnancy with Nerivio (Nerivio group), to women with migraine who did not treat migraine attacks during pregnancy with Nerivio (control group). Nerivio group participants will be recruited from Theranica's user base. Control group participants will be recruited by health care providers, including headache specialists and OBGYNs (study co-investigators). The study is fully electronic, including an e-eligibility questionnaire, an e-ICF, and an e-survey. Participants will be compensated for their time.

Goal

Assess the safety of treating migraine with Nerivio during pregnancy and 3 months postpartum.

Study Design

Retrospective controlled survey-study.

Study group: Postpartum patients with migraine who used Nerivio at least 3 times during their "study pregnancy"

Control group: Postpartum patients with migraine who did not use Nerivio during their "study pregnancy"

Eligibility

Inclusion criteria:

- 1. Diagnosed with migraine
- 2. History of migraine pre-pregnancy with an average of at least 4 migraine days per month, in the six months prior to the last pregnancy
- History of pregnancy with last menstrual period (LMP) between November 1st, 2019 –
 March 31st, 2021. Pregnancy within this time window is the pregnancy of study, termed
 "study pregnancy"
- 4. Between 18 and 42 years of age at first day of the last menstrual period (LMP) of "study pregnancy"
- 5. History of at least 4 migraine attacks during "study pregnancy"
- 6. In the study group: usage of Nerivio for at least 3 treatments (≥30 minutes/treatment) during "study pregnancy"
- 7. In the control group: No history of using Nerivio, ever

TCH-011 Clinical Study Protocol

Doc ID: TECXXXX

Revision #: 1.0

Page: 5 of 25

Exclusion criteria:

- 1. History of preterm birth (gestational age at deliver<37 weeks) in previous pregnancies prior to the "study pregnancy"
- 2. History of congenital malformations or birth defects in previous pregnancies prior to the "study pregnancy"

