- 3. Severe other diseases which started before the "study pregnancy" and lasted into the "study pregnancy" period, including congenital heart disease, arrhythmia, history of myocardial infarction (MI), history of stroke, or active cancer
- 4. Serious physical injury that occurred during the "study pregnancy": severe car collision injury, serious injury at home/work, etc. Multiple gestation (i.e., pregnancy with more than one baby at a time, such as pregnancy with twins, triplets, and quadruplets) in the "study pregnancy"

Study Design and Recruitment

Study group: Study group participants will be recruited from Nerivio's user base. An invitation message will be sent via in-app notification and/or email to all Nerivio users who are (1) female, AND (2) between 18 and 42 years of age as of November 1st, 2019 - March 31st, 2021. Users who meet these criteria will be invited to fill in a screening and eligibility questionnaire. If they meet the eligibility criteria, they will be offered the opportunity to participate in the study. Participants will complete and sign an electronic informed consent form. Following consent, participants will be asked to complete the questionnaire. Once complete, participants will be compensated for their time.

Control group: Control group participants will be referred to the study by site co-investigators, who are US licensed healthcare providers seeing women with headache disorders and/or women during their pre-pregnancy and/or pregnancy period. Patients interested in participating will be directed to the same screening and eligibility questionnaire and will follow the same study design.

Endpoints

Endpoints focus on the health of the mother and the baby, during pregnancy and three months postpartum.

Primary endpoint:

Demonstrate that the study group is not different than the control group in regard to gestational age at delivery (measured in pregnancy weeks).

QMS document

TCH-011 Clinical Study Protocol

Doc ID: TECXXXX

Revision #: 1.0

Page: 6 of 25

Secondary endpoints:

Demonstrate that the study group is not different from the control group in:

- 1. Baby's birth weight (average birth weight)
- 2. Miscarriage rate (% of miscarriage cases)
- 3. Preterm birth rate (% cases of preterm pregnancies, as measured in % of pregnancy weeks less than 37)
- 4. Birth deficits rate (% of birth deficits)
- 5. Still births rate (% of still births)

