- 6. Meeting developmental milestones following 3 months postnatal (% of babies)
- 7. Visits to the emergency room or urgent care due to pregnancy and/or migraine symptoms during pregnancy and 3 months postpartum period (# of events)

Exploratory endpoints: Difference between the study group and the control group in:

- 1. Overall subjective **feeling of safety** using acute migraine treatments during pregnancy (in subjects who used such treatments).
- 2. Overall subjective **satisfaction** with the acute migraine therapies used during the pregnancy (in subjects who used such treatments).
- 3. APGAR score at 5 minutes.

Data analysis

Statistical Hypothesis

The goal of the proposed study is to test the null hypothesis that treating with Nerivio during pregnancy does not impose a safety risk relative to standard care migraine treatment for pregnant women. In other words, the hypothesis is that the means of the two populations are equal. Thus, in this study, the following hypotheses will be tested:

• Null hypothesis: H0: GAt = GAc

• Alternate hypothesis: H1: GAt ≠ GAc

Where GAt and GAc are the average Gestational Age in the study group and control group, respectively. If the null hypothesis is not rejected, the study will be deemed successful. The criterion for significance has been set at 0.05. The test is 2-tailed.

TCH-011 Clinical Study Protocol

Doc ID: TECXXXX

Revision #: 1.0

Page: 7 of 25

Planned Sample Size

Based on USA data from 2020 [Osterman M, et al. Births: Final Data for 2020. Natl Vital Stat Rep. 2021] we assume mean gestational age (GA) of 38.4 with standard deviation of 2.7 (range 26-42).

With the proposed sample size of 114 for each group, the study will have power of 80% to yield a statistically significant result. This computation assumes that the mean difference is less than 1.0 week, and the common within-group standard deviation is 2.7. This effect was selected as the smallest effect that would be important to detect.

Precision for estimating the effect size: We further estimate the mean difference between the two populations. On average, a study of this design would enable us to report the mean difference with a precision (95% confidence level) of plus/minus 0.70 weeks.

Given this statistical requirement up to 400 participants will be recruited per group.

Statistical Analysis Plan

Data will be collected from all patients recruited to the study. Data analysis will not include patients who are:

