- Obese (BMI>=40) at the beginning of the study pregnancy
- Did not have their last menstrual period (LMP) between November 1st, 2019 March 31st, 2021
- In the study group, did not use Nerivio for at least 3 treatments (≥30 minutes/treatment) during the "study pregnancy"
- In the control group, did use Nerivio before, during, or in the 3 months following the "study pregnancy"

TCH-011 Clinical Study Protocol

Doc ID: TECXXXX

Revision #: 1.0

Page: 8 of 25

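### Only the Nerivio group must stay pregnant until a third treatment, and women with one or two uses are analysed in neither group, which can mask harm on the miscarriage endpoint

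*Combined protocol and SAP*

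**What the plan says.** Inclusion criterion 5 applies to everyone: "History of at least 4 migraine attacks during" the study pregnancy, checked by Question 8 of Appendix 1. Criterion 6 begins "In the study group: usage of" and so adds a condition, three Nerivio treatments, for one group only. The Statistical Analysis Plan repeats it as an analysis exclusion: study-group women who did not "use Nerivio for at least 3 treatments (≥30 minutes/treatment) during the" study pregnancy are left out. Criterion 7 requires controls never to have used Nerivio, and the analysis exclusions remove controls with any use before, during or in the three months after the pregnancy.

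The secondary endpoints are introduced by "Demonstrate that the study group is not different from the control group in", and the second is "Miscarriage rate (% of miscarriage cases" as a percentage. Appendix 2 can record early losses: Question 20 accepts pregnancy lengths from 6 weeks, and Questions 21 and 22 cover miscarriage and its cause. Questions 27 and 28 ask, yes or no, about any Nerivio use and about three or more uses in the pregnancy. Neither asks when the device was used. No landmark or other timing-based analysis is planned.

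**The concern.** A woman who uses Nerivio once or twice and then miscarries was exposed, yet her loss is counted nowhere. A comparable woman who never used the device counts as a control once she has had four attacks. The Nerivio group is thus selected for surviving longer in pregnancy whenever the third treatment comes after the fourth attack.

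The endpoint is a safety outcome that the plan hopes to show is the same in both groups. A bias that tends to lower the exposed group's loss rate favours that conclusion, and a true excess could be reduced or hidden.

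**Working it through.** **The plan's own figures.** None is given for miscarriage. The primary sample size reproduces: n = 2 × (1.96 + 0.842)² × 2.7² / 1.0² = 114.4, against "With the proposed sample size of 114 for each group"; precision is 1.96 × 2.7 × √(2/114) = 0.70 weeks, as stated. It says nothing about the loss rate.

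**Inputs from the documents.** At least 4 attacks in both groups; at least 3 treatments in the study group; births with mean 38.4 weeks, SD 2.7, range 26 to 42.

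**Assumed inputs.** 10% of pregnancies lost, at week 6 + Gamma(shape 2, scale 2); a fixed attack rate counted from LMP; a fixed share s of attacks treated, one treatment per attack; no device effect.

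**Formulas.** Attacks by week t are Poisson with mean m = (attacks per month) × (12/52) × t. Treated attacks are Poisson(m·s) and untreated attacks Poisson(m(1 − s)), independently. Let e_L and e_B be the probabilities of meeting the entry rule before a loss and before a birth, averaged over the ending week. Then

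observed loss rate = 0.1·e_L / (0.1·e_L + 0.9·e_B).

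Controls need attacks ≥ 4. The study group needs attacks ≥ 4 and treated ≥ 3.

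Example, 4 attacks a month and 25% treated:
- Control: 0.1 × 0.957 / (0.0957 + 0.9 × 1.000) = 9.6%.
- Nerivio: 0.1 × 0.396 / (0.0396 + 0.9 × 0.992) = 4.2%.
- Ratio: 0.44.

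| Attacks/month | Control rate | Share treated | e_L | e_B | Nerivio rate | Ratio (≥3 uses) |
|---|---|---|---|---|---|---|
| 2 | 6.6% | 25% | 0.115 | 0.810 | 1.55% | 0.24 |
| 2 | 6.6% | 50% | 0.376 | 0.992 | 4.0% | 0.61 |
| 2 | 6.6% | 75% | 0.570 | 1.000 | 6.0% | 0.90 |
| 4 | 9.6% | 25% | 0.396 | 0.992 | 4.2% | 0.44 |
| 4 | 9.6% | 50% | 0.795 | 1.000 | 8.1% | 0.84 |
| 4 | 9.6% | 75% | 0.931 | 1.000 | 9.4% | 0.98 |
| 8 | 10.0% | 25% | 0.798 | 1.000 | 8.1% | 0.81 |
| 8 | 10.0% | 50% | 0.985 | 1.000 | 9.9% | 0.99 |
| 8 | 10.0% | 75% | 0.999 | 1.000 | 10.0% | 1.00 |

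Ratios use unrounded values. At 100% treated the two entry rules coincide and the ratio is 1.00.

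**Other loss timing.** With 15% losses over weeks 4 to 20, a weekly hazard falling by a factor of 0.85, and one attack a week counted from LMP, the ratios at 25/50/75/100% are 0.44/0.81/0.96/1.00.

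**A true doubling (20% loss in device users), 4 attacks a month.** Without the three-treatment rule, 9.6% against 19.3% would be seen. With it and 25% treated, the Nerivio rate is 0.2 × 0.396 / (0.0792 + 0.8 × 0.992) ≈ 9%, which is no visible excess. At 50% treated it is 0.2 × 0.795 / (0.159 + 0.8) ≈ 16.6%. The recruitment ceiling is stated thus: "Given this statistical requirement up to 400 participants will be recruited per group". If 400 per group were analysed, power to see an excess (two-sided 0.05) would be about 97% without the rule, against 1% (25% treated) or 83% (50% treated). At 114 per group it is 55%, against 2% or 34%.

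**Reversals.** Suppose half the women treat 5% of attacks with 7% loss risk and half treat 90% with 13%. At 4 attacks a month the observed rate goes from 9.6% in controls to 10.1% in the study group; at 8 a month it goes from 10.0% to just over 8.2%. If half the women have 1 attack a month and half have 15, with 25% treated, the ratio is 1.17.

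**Pooled any use (treated ≥ 1), 25% treated.**
- 2 a month: 0.1 × 0.507 / (0.0507 + 0.9 × 0.987) = 5.4%; ratio 0.82, up from 0.24.
- 4 a month: 0.1 × 0.861 / (0.0861 + 0.9 × 1.000) = 8.7%; ratio 0.91, up from 0.44.

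**One or two uses as a separate group, 25% treated.**
- 4 a month: e_L = 0.861 − 0.396 = 0.465 and e_B = 0.9998 − 0.9917 = 0.0081, so the loss rate is 0.0465 / (0.0465 + 0.0073) ≈ 86%, against 9.6% in controls.
- 2 a month: about 20%, against 6.6%.

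Both arise with no device effect.

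**The case against.** The strongest reply is that the size rests wholly on inputs the documents do not give. At 75% treated the ratio is 0.90 or higher in the table, and at 8 attacks a month with half treated it is 0.99. More than one treatment per attack would shrink the bias further. The common four-attack rule already asks some survival of controls. Miscarriage is one of seven secondary endpoints, and the success rule rests on gestational age. All of this stands, and it limits the weight of the point. It does not remove the asymmetry, which follows from the text alone. Low attack rates are also possible under the plan: the minimum of four migraine days a month applies before pregnancy, during pregnancy only four attacks in total are needed, and Questions 29 to 34 offer a category below four a month.

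A reader might infer that the Nerivio rate must be too low. The documents do not support that. The reversals above show that the direction needs the stated conditions. The groups are also recruited by different routes, Nerivio's user base and referring providers, with effects on loss rates that cannot be quantified here.

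A reader might also infer that the primary endpoint is compromised. If gestational age is analysed in births, the same rule shifts its mean by at most about 0.1 weeks in these models, which is not material.

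**Conclusion.** The concern holds as a conditional bias. At a given attack rate, if the share of attacks treated is unrelated to loss risk, the three-treatment rule lowers the Nerivio miscarriage rate or leaves it unchanged. The illustrative no-effect ratio runs from about 0.24 (2 attacks a month, 25% treated) to 1.00 (every attack treated). It is far from 1 only when attacks are few or a minority are treated. These figures assume 10% losses, the stated loss timing, one treatment per attack and no variation between women. They do not predict this study's result, and the net bias is unknown.

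The plan should be changed because the affected claim is one of safety and part of the remedy uses data already collected. It would go too far to say that losses are not captured because the appendices speak of the latest completed pregnancy: Questions 20 to 22 accept them. That wording is a separate, minor clarification.

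**What to change.** 1. Amend the analysis exclusion, with a note in criterion 6, so that women answering Yes to Question 27 and No to Question 28 are retained for one pre-specified analysis: miscarriage in women with any use (one or more), pooled, against controls, beside the planned comparison of three or more uses. The screening questionnaire does not ask about Nerivio, so these women can reach the survey as it stands. This reduces the bias without removing it.

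2. Do not compare the women with one or two uses with controls as a separate group. Few uses is partly a result of early loss, so they would show a high loss rate with no device effect. If their counts are listed, say so beside them.

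3. Because the timing of use is not collected and some bias remains, report miscarriage descriptively: counts, and the difference with its 95% CI, without a claim of no difference. At 10% losses in both groups the half-width is 1.96 × √(2 × 0.1 × 0.9 / n), which is 7.8 percentage points at 114 per group and 4.2 at 400.

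The cost is one extra analysis, a short amendment and one secondary claim given up. The number of women with one or two uses may be small.

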Appendix 1: Screening and Eligibility Procedure

Thank you for your interest in this study. We will be assessing the effect of having migraine and using Nerivio, an acute migraine treatment, on the health of mothers and babies during pregnancy and 3 months postpartum, in mothers who suffer from migraine.

To assess your eligibility for the study, please answer the following screening questions.

If you meet the eligibility criteria, you will be directed to an electronic informed consent form, followed by the study questionnaire.

Eligible participants who complete the study questionnaire will be compensated for their time, with a \$100 gift card.

The following questions refer to your latest, completed, pregnancy (if you are currently pregnant, do not refer to the current pregnancy when answering the following questions). We will refer to that pregnancy (i.e., the completed pregnancy) as the "study pregnancy".

Page break

- 1. Was your entire "study pregnancy" period (from conception to delivery) between November 1st, 2019, and March 31st, 2022?
 - Yes
 - No

No = not eligible

- 2. Were you between 18 and 42 years of age when your "study pregnancy" began (at the date of the last menstrual period, LMP)?
 - Yes
 - No

No = not eligible

- 3. Did the "study pregnancy" have more than one baby, such as pregnancy with twins, triplets, and quadruplets (i.e., multiple gestation pregnancy)
 - Yes
 - No

Yes = not eligible

4. Have you ever diagnosed with migraine by a licensed healthcare provider?

QMS document

TCH-011 Clinical Study Protocol

Doc ID: TECXXXX
Revision #: 1.0

Page: 9 of 25

	• Yes
	• No
	No = not eligible
5.	Were you diagnosed with migraine prior to your "study pregnancy"?
	• Yes
	• No
	No = not eligible
6.	Did you have migraine attacks during your "study pregnancy"?
	• Yes
	• No
	No = not eligible
7.	On average, did you have migraine at least 4 days a month, during the six months prior to the "study pregnancy"?
	• Yes
	• No
	No = not eligible
8.	Did you have at least 4 migraine attacks during your "study pregnancy"?

- a. Voc
 - Yes
 - No

No = not eligible

- 9. Did you suffer from congenital heart disease, arrhythmia, history of myocardial infarction (MI), history of stroke, or active cancer before/during the "study pregnancy"?
 - Yes
 - No

Multiple choice; If Yes = not eligible

- 10. Were you seriously injured during your "study pregnancy", e.g., had a car accident, work injury, home accident, assault, etc.?
 - Yes

TCH-011 Clinical Study Protocol

Doc ID: TECXXXX

Revision #: 1.0

Page: 10 of 25

No

Yes = not eligible

- 11. Do you have a history of preterm birth (delivery at gestational age under 37 weeks) with any of your previous pregnancies (before the "study pregnancy")?
 - Yes
 - No

Yes = not eligible

- 12. Do you have a history of congenital malformations or birth defects in any of your previous pregnancies (before the "study pregnancy")?
 - Yes
 - No

Yes = not eligible

Eligibility messages:

Not eligible message: Message presented to subjects if they do **not meet** the eligibility criteria as identified during the screening questionnaire:

Thank you for your interest in the study on migraine treatments during pregnancy. However, the information you provided indicates that you do not meet the study eligibility requirements, and therefore cannot participate in this survey study.

Eligible message: Message presented to subjects upon the completion of the screening questionnaire, if they **meet** the eligibility criteria as identified during the screening questionnaire:

Thank you for your interest in the study on migraine treatments during pregnancy.

The information you provided indicates that you are eligible to participate in this survey study.

You will now be directed to an electronic informed consent form. Please read the consent form carefully. If you consent, please provide your details and electronic signature at the bottom of the consent form.

Once signed, you will be directed to the survey study questionnaire.

The questionnaire contains 52 questions. It should take approximately 30-40 min to complete the questionnaire.

In order to make it easier and faster to answer the survey questions, we recommend you prepare documents you received upon hospital discharge following delivery of your "study pregnancy", prior to answering the questionnaire.

Please select your referral clinic:

QMS document

TCH-011 Clinical Study Protocol

Doc ID: TECXXXX
Revision #: 1.0

Page: 11 of 25

- 1. Clinic A
- 2. Clinic B
- 3. Clinic C
- 4. Clinic D
- 5. Clinic E
- 6. Other

Single choice

Present the matching ICF, based on participant's clinic

QMS document

TCH-011 Clinical Study Protocol

Doc ID: TECXXXX

Revision #: 1.0

Page: 12 of 25

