TCH-011 Clinical Study Protocol

Doc ID: TECXXXX
Revision #: 1.0

Page: 16 of 25

PIO	locoi	

- Botox® injection for migraine prevention (Botulinum toxin)
- Aimovig[®] (Erenumab)
- Ajovy® (Fremanezumab)
- Emgality® (galcanezumab-gnlm)
- Vyepti® (eptinezumab-jjmr)
- Nurtec® ODT (Rimegepant)
- Devices (e.g., gammaCore, Cefaly)
- Other
- Did not use any preventive treatment

Check all that applies

- 12. Have you been diagnosed with migraine with aura by a licensed healthcare provider? (Aura is a neurologic symptom that occurs typically before or during migraine that lasts 5-60 minutes and is characterized by an evolution of neurologic symptoms such as flashing lights or colors that grow in your visual field)
 - Yes
 - No
- 13. Do you usually experience aura right before your headache attacks?
 - Always
 - Sometimes
 - Never
- 14. Have you ever used Nerivio® to treat your migraine attacks?
 - Yes
 - No
- 15. How many prior pregnancies before the "study pregnancy" have you had?

Choose from 0 to 10 and "more than 10"

16. How many of these were completed pregnancies?

QMS document

TCH-011 Clinical Study Protocol

Doc ID: TECXXXX

Revision #: 1.0

Page: 17 of 25

Show question if >0 in the previous question. Responses: Choose from 0 to 10 and "more than 10"

- 17. Is there a family history of congenital defects or malformations?
 - Yes
 - No

Part 2 – Study pregnancy

The following questions refer to you latest, completed, pregnancy, termed "study pregnancy" (if you are currently pregnant, please do not refer to this pregnancy when answering the questionnaire).

- 18. What was the first day of the last menstrual period (LMP) before your "study pregnancy"? (Please provide accurate month and year. If you do not recall the exact day within the month, please choose 1st day of the month).
 - Choose on calendar / enter date (month, year; day is optional)

Year and month are good enough. Day is optional.

- 19. What was the delivery date of your "study pregnancy"?
 - Choose on calendar
- 20. What was your baby's gestational age at delivery or at the end of pregnancy (pregnancy length measured by number of weeks and days) of your "study pregnancy"

Choose on "roller", allow weeks (6 to 42 weeks) and days (+0 to 6 days). If possible, allow weeks and days separately..

- 21. What is the status of your "study pregnancy"?
 - Live birth
 - Elective termination
 - Spontaneous abortion (or miscarriage)
 - Late fetal death

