- 22. If you had a miscarriage, what was its cause?
 - I did not experience a miscarriage
 - Abnormal fetal development

QMS document

TCH-011 Clinical Study Protocol

Doc ID: TECXXXX

Revision #: 1.0 Page: 18 of 25

- Abnormal placenta (such as abruption)
- Blood disorders such as thrombophilias
- Cervical insufficiency
- Chromosomal abnormalities
- Maternal anatomic abnormalities such as uterine fibroids, polyps or adhesions in uterus
- Physical trauma
- Unknown cause
- Other

23. Delivery circumstances (Check all that applies)

- Spontaneous labor
- Induction of labor
- Past due date
- Decreased fetal movement
- Cardiac arrhythmia in fetus
- Pregnancy induced hypertension such as gestational hypertension or pre-eclampsia
- HELLP syndrome
- Premature rupture of membranes
- Other complications or medical concerns

Check all that apply

24. What was the mode of delivery?

- Repeat Cesarean Delivery
- Primary Cesarean delivery
- Spontaneous vaginal delivery

25. During your "study pregnancy", did you do any of the following (select all that apply)

Smoking

QMS document

TCH-011 Clinical Study Protocol

Doc ID: TECXXXX Revision #: 1.0

Page: 19 of 25

•	Excessively consuming alcohol (more than 1 glass of wine/day or any other
	equivalent)

- Using recreational drugs

Using medical marijuana

Check all that apply

26. Was the baby discharged from the hospital at the same time with yo	u?
--	----

- Yes
- No
- 27. Did you use Nerivio to treat your migraine attacks during your "study pregnancy"?
 - Yes
 - No
- 28. During your "study pregnancy", did you use Nerivio for migraine treatment at least 3 times?
 - Yes
 - No

Part 3 – Migraine during the study pregnancy

The following questions refer to your latest, completed, pregnancy referred to as the "study pregnancy" (if you are currently pregnant, please do not refer to this pregnancy when answering the questionnaire).

- 29. How many migraine days per month (on average) did you have during the FIRST trimester of your "study pregnancy"?
 - Less than 4 days per month
 - 4-8 days per a month
 - 9-14 days per month
 - 15 days or more per month

Multiple choice

30. How often did you use ACUTE treatments for migraine during the FIRST trimester of your "study pregnancy"?

QMS document

TCH-011 Clinical Study Protocol

Doc ID: TECXXXX

Revision #: 1.0

Page: 20 of 25

- Less than 4 times per month
- 4-8 times per a month
- 9-14 times per month
- 15 times or more per month

Multiple choice

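### The study pregnancy is defined inconsistently, so miscarriages and stillbirths followed by a later completed pregnancy are not captured, and both rates are likely recorded too low

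*Combined protocol and SAP*

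**What the plan says.** **By LMP window.** Inclusion criterion 3 sets an LMP window of 1 November 2019 to 31 March 2021 and adds: "Pregnancy within this time window is the pregnancy of study". The Statistical Analysis Plan applies the same window by dropping women who did not "have their last menstrual period (LMP) between November 1st, 2019" and 31 March 2021.

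**By order.** Appendix 1 tells the respondent to think of her latest completed pregnancy and says "We will refer to that pregnancy (i.e., the completed pregnancy) as the" study pregnancy. Appendix 2 repeats this, for example at the start of Part 3: "The following questions refer to your latest, completed, pregnancy referred to as the" study pregnancy. Inclusion criterion 2 also leans this way, because it anchors baseline migraine frequency to the last pregnancy.

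**Screening.** Question 1 asks whether the whole study pregnancy "period (from conception to delivery) between November 1st, 2019, and March 31st, 2022"; No means not eligible. Question 11 excludes women with a preterm birth in any earlier pregnancy.

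**Outcomes.** The secondary endpoints include "Miscarriage rate (% of miscarriage cases") and the stillbirth rate, both with the aim of showing that the groups do not differ. Survey Questions 20 to 22 record length, outcome and cause of loss for the study pregnancy only. For earlier pregnancies, Question 15 asks how many there were and Question 16 asks: "How many of these were completed pregnancies".

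**The concern.** Participants see only the forms, so the forms decide which pregnancy is reported. A woman who lost a pregnancy in the window and later completed another must describe the later one. Her loss is then missing from endpoints 2 and 5.

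Miscarriage and stillbirth are core outcomes in a study of safety in pregnancy. Missing events lower both rates and shrink the absolute difference between groups, so a real harm is harder to see, and the stated aim is to show no difference. The analyst cannot recover the events by filtering on Question 21, which covers one pregnancy per woman.

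Two other wordings may discourage women with a loss from enrolling. Both groups are described as "Postpartum patients with migraine who" did or did not use the device, and screening Question 1 runs to delivery with no answer for a pregnancy that ended otherwise.

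**Working it through.** **The plan's own figure.** The only sample-size figure concerns gestational age. 2 × (1.96 + 0.842)² × 2.7² / 1.0² gives 115 per group against the stated 114, so it reproduces, but it does not bear on this point. The plan states no rate or power for miscarriage or stillbirth.

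**Where a loss in the window goes if a later pregnancy has been completed by the survey**

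| Later pregnancy | What happens | Loss recorded as an outcome? |
|---|---|---|
| LMP also in the window | Later pregnancy reported instead | No |
| LMP after 31 March 2021, ended by 31 March 2022 (at 40 weeks, LMP up to 24 June 2021) | Passes Question 1, removed by the SAP filter | No |
| Ended after 31 March 2022 | Rejected by Question 1 | No |
| Any, after an earlier preterm stillbirth | May be rejected by Question 11 | No |

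**Direction.** Let *m* be the true loss rate among pregnancies with LMP in the window, and *f* and *g* the shares of losses and of births superseded by a later completed pregnancy. Then

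recorded rate = m(1−f) / [m(1−f) + (1−m)(1−g)],

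which is below *m* exactly when f > g. With assumed m = 15% and g = 10%:

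- f = 20%: 0.120 / (0.120 + 0.765) = 13.6%
- f = 40%: 0.090 / (0.090 + 0.765) = 10.5%
- f = 60%: 0.060 / (0.060 + 0.765) = 7.3%
- reverse case, f = 10% and g = 30%: 0.135 / (0.135 + 0.595) = 18.5%

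**Time available, from the plan's dates.** The window has 517 LMP dates, on average 258 days after 1 November 2019. 31 March 2022 is day 881. A later pregnancy of 38.4 weeks (the plan's mean) takes 269 days. Mean room = 881 − 258 − length of the first pregnancy − 269.

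- Loss at 10 weeks (70 days): 284 days; a later pregnancy fits for all 517 dates.
- Loss at 20 weeks (140 days): 214 days; it fits for 473 of 517 (91%).
- Birth at 38.4 weeks (269 days): 85 days; it fits for 344 of 517 (66.5%).

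With negative room set to zero, the last two means are 216 and 114 days.

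**Illustrative size.** Successive pregnancies were simulated with an 8% loss rate. The next LMP came 1 month plus an exponential time after a loss, and 3 months plus an exponential time at 2% per month after a birth. The table gives recorded divided by true miscarriage rate for losses at 10 to 20 weeks. The share conceiving within 12 months of a loss is 1 − exp(−11 × monthly rate).

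| Monthly rate after a loss | Share in 12 months | Survey 31 March 2022 | Survey end 2022 |
|---|---|---|---|
| 2% | 20% | 0.89–0.93 | 0.85–0.89 |
| 4% | 36% | 0.76–0.83 | 0.62–0.67 |
| 6% | 48% | 0.66–0.75 | 0.45–0.52 |
| 10% | 67% | 0.52–0.63 | 0.24–0.31 |

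For stillbirth at 30 weeks (assumed rate 2%, survey 31 March 2022) the factors are 0.96, 0.88, 0.82 and 0.73. The first row uses the same monthly rate after losses and births, and the factor is still below 1. With 2% after a loss and 4% to 6% after a birth, and a survey at end 2022, it is about 1.00 to 1.20.

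**Effect on detection.** Take assumed true miscarriage rates of 5% and 10%, and a two-sided 0.05 normal approximation. At 400 per group with all losses recorded, the null SE is √(2 × 0.075 × 0.925/400) = 0.0186 and the alternative SE is √(0.1375/400) = 0.0185. Power is Φ[(0.05 − 1.96 × 0.0186)/0.0185] = 77%. It is 66% if both rates are multiplied by 0.8 and 46% at 0.5. At 114 per group the figures are 30%, 24.5% and 17%.

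**The case against.** **The two definitions may be one rule.** Criterion 2 also refers to the last pregnancy, so the intention may be the latest completed pregnancy, eligible if its LMP is in the window. That is a fair reading, but criterion 3 does not say it, and the rule still loses every superseded loss.

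**A reader might infer that the rates are certainly too low.** The documents do not support certainty. The direction needs losses to be superseded more often than births, and no such rates are given. The reverse would need births to be superseded more often despite having less time left. That is possible but less plausible.

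**A reader might infer that no loss can enrol, because Question 1 ends at delivery.** The survey points the other way. Question 20 accepts lengths from 6 weeks and refers to the end of pregnancy, Question 21 lists miscarriage and late fetal death, and Question 22 asks for a cause. Losses were meant to enrol; Question 1 is loosely worded.

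**A reader might infer that superseded losses leave no trace.** Questions 15 and 16 do count earlier pregnancies, and women removed by the SAP filter have still given data. But date, outcome type and device exposure are missing, so a loss cannot be placed in the window or attributed to a group.

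**A reader might infer a false difference between groups**, since one is recruited from a user base and the other through clinicians. Reconception could differ, but nothing in the documents shows that it does.

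**Study success rests on gestational age alone.** True. Endpoints 2 and 5 have no stated power, and the 5% v 10% example has only 30% at 114 per group even with every loss recorded. The point concerns how these two safety endpoints may be interpreted.

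**Conclusion.** The inconsistency is in the text and does not depend on any assumption, and neither does the failure to capture losses superseded by a later completed pregnancy. That the miscarriage and stillbirth rates come out too low is likely rather than proven; it rests on losses being superseded more often than births, which the plan's own dates make probable. The size cannot be fixed from the documents. For miscarriage, a factor of about 0.5 to 0.9 is an illustration for losses at 10 to 20 weeks, a survey on 31 March 2022 and the assumed reconception rates; a later survey widens the range. The rule requiring at least four attacks during the pregnancy already makes very early losses less likely to qualify. Gestational age among births is not challenged here.

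**What to change.** Use one definition in the protocol, the SAP and both forms. One workable version: *the study pregnancy is the first pregnancy with LMP from 1 November 2019 to 31 March 2021 that meets the eligibility criteria, whatever its outcome and whether or not another pregnancy followed.* Other rules are possible, provided they do not depend on outcome or on later pregnancies and say what happens when two pregnancies fall in the window.

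Then:

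- replace the latest-completed wording in Appendices 1 and 2 and the last-pregnancy wording in criterion 2;
- reword screening Question 1 to run *from last menstrual period to the end of the pregnancy (birth, miscarriage, stillbirth or termination)*;
- describe both groups as women whose study pregnancy has ended, in place of postpartum patients.

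Under this definition a stillbirth in an eligible window pregnancy is itself the study outcome, so Question 11 no longer screens it out as history.

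**Cost.** Before recruitment this is wording only, with no new data items. Women with a later pregnancy must recall an earlier one, so recall error rises somewhat. If the survey has closed, the missing details cannot be recovered from it; report the likely under-capture and do not use endpoints 2 and 5 to conclude that the groups do not differ.
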